Venous catheter insertion, which is less invasive than arterial catheterization, can be associated with bruising, infection, or clot formation. Using proper placement techniques will minimize these risks.

c. Arterial and venous sampling

Blood draw volumes will not exceed the limits allowed by the NIH Clinical Center (Medical Administrative Policy M95-9: Guidelines for Blood Drawn for Research Purposes in the Clinical Center); in this study, the volume of blood drawn will not exceed 230 mL per scan. Blood sampling may lead to the formation of a small subcutaneous hematomas caused by blood leaking from a punctured blood vessel. Such hematomas cause only minor discomfort. They are not dangerous and require no treatment other than reassuring the patient. There is also a small risk of infection at the site of the needle puncture, which can be readily treated with antibiotic therapy. Subjects will be asked not to donate blood for a period of eight weeks after participation is completed.

d. MRI

Three-Tesla MRI is widely used as a clinical imaging tool. Subjects will be screened and excluded for the presence of any metallic prostheses both at the time of recruitment and just prior to the MRI. Subjects will wear earplugs to minimize exposure to excessively loud noises. Occasionally subjects become anxious during the scan. In that case, lorazepam (0.5–1 mg) or a comparable benzodiazepine anti-anxiety agent may be

given orally before the MRI as requested by subjects, and if not clinically contraindicated. Subjects can also request that the operator stop the scan at any time. Side effects of anti-anxiety medications may include prolonged sedation (usually less than eight hours), lightheadedness, lassitude, motor incoordination, and difficulties with balance. These effects are transient and go away after several hours. Subjects will be instructed to not drive, handle machinery, or drink alcohol until the next day. Subjects who receive a sedative will be observed in clinic until the sedation wears off and will be required to bring a driver or will be provided a taxi home.

Severely claustrophobic subjects find it difficult to undergo MRI scans; thus, such subjects will be excluded at the time of recruitment.

e. Radiation exposure

Radiation exposure in this protocol will be from $[^{11}C](R)$ -rolipram and transmission scans for PET using ⁶⁸Ge or ¹³⁷Cs source or CT transmission for PET/CT. Among these three types of transmission scans, CT transmission causes the highest radiation as calculated by [name], CC PET Dept., July 22 2015; according to ICRP103. Therefore, the radiation exposure from CT transmission is used to calculate total radiation exposure in 88-23(a). Radiation dose estimates for $[^{11}C](R)$ -rolipram are based upon biodistribution data in healthy human subjects performed by the MIB, NIMH under protocol 06-M-0002 "PET whole body biodistribution and test retest brain imaging studies using a phosphodiesterase 4 inhibitor (R)- $[^{11}C]$ rolipram" (PI: [name], MD, PhD). That study showed that the highest effective dose in this protocol is about four rem for patients with MAS and healthy controls who would undergo one brain scan and two whole-body scans with two CT transmission scans for each brain and whole-body scan, respectively. Although CT transmission scans have higher radiation exposure than ⁶⁸Ge or ¹³⁷Cs transmission scans, CT transmission scans are far more commonly performed in both clinical and research settings because they are the only choice for PET/CT scanners. This amount is within NIH RSC guidelines. Detailed results of this dosimetry study are included in the attached NIH 88-23(a). In case the subject moves between the transmission scan and the injection of $[^{11}C](R)$ -rolipram, the MIB routinely includes two transmission scans for each PET scan to allow a repeat of transmission. Note: the designation of radiation dose of "about four rem" was recently approved by the Radiation Safety Committee as an alternative way to present risk to patients using rounded numbers, which better reflects the actual dose to an individual subject.

All subjects will be asked about any prior research participation involving radiation exposure so that the total exposure, in combination with the present study, will not exceed an effective dose of five rem per 12 months. Examples may include mammograms, x-rays taken in radiology departments, cardiac catheterization, and fluoroscopy as well as nuclear medicine scans in which radioactive materials were injected into your body.

f. PET scan

PET scanning, which detects injected radioactivity within the body, has been used as a clinical imaging tool. We routinely use a series of procedures to minimize the risk of discomfort during scanning sessions. Namely, the procedures are conducted in the presence of trained health professionals to whom subjects will have ready access should they experience any problems. Subjects can communicate with the trained health professionals while in the scanner and can be removed from the scanner or withdraw from the study at any time if they wish to do so.

Occasionally subjects become anxious during the scan. In that case, subjects can request that the operator stop the PET scan.

g. Roflumilast administration

Roflumilast is an FDA approved PDE4 inhibitor, used commonly to treat COPD. In this study, subjects may receive a single dose of 500 µg roflumilast P.O. For treatment of COPD, roflumilast is normally given at a dose of 500 µg over a period of weeks or months (15). Therefore, we feel that the risks of serious reactions are low given that we are administering only a single dose. Adverse reactions to roflumilast administration reported by $\geq 2\%$ of patients (n = 4438) include: diarrhea, weight loss, nausea, headache, back pain, influenza, dizziness, and decreased appetite. Psychiatric disorders (anxiety, depression) occurred at a frequency of 1 to 2% greater than placebo. We will contact all patients who receive roflumilast 24-48 hours after its administration to confirm they are feeling well.

8. Subject Safety Monitoring

Participants will be carefully monitored by clinical staff throughout the study. Participants will be asked about the presence of adverse events throughout the procedure. To confirm the absence of the pharmacological effects of the PET ligand, for each PET scan, a clinically credentialed investigator will monitor vital signs within three hours before tracer injection, and again at approximately 30 and 90 minutes after radioligand injection. The site of the arterial and venous catheter insertion will be carefully monitored for signs of bleeding during the PET scans and also after removal of the catheter.

All adverse events (AEs) will be recorded on the case report form. All AEs, including clinically significant abnormal findings on laboratory evaluations, regardless of severity, will be evaluated until satisfactory resolution. After removal of venous lines, the site of the catheter insertion will be carefully monitored for signs of bleeding.

Toxicity tables/criteria to be used

Toxicity will be assessed according to the NCI Common Terminology Criteria for Adverse Events (CTCAE) v.4.03 http://evs.nci.nih.gov/ftp1/CTCAE/About.html.

Criteria for individual subject withdrawal

We will stop study procedures for any subject with any Grade 2, Grade 3, or greater non-laboratory toxicity that is intolerable, persistent, or uncorrectable for more than several minutes. In addition, the Medical Advisory Investigator or a clinically credentialed investigator may terminate study procedures based on clinical judgments. Likely causes are pain at the site of catheter insertion and difficulties to stay in MRI and PET scanners, and the judgement of withdrawal by study investigators will be done as described above. In addition, study participants can voluntarily withdraw at any time for any reason.

9. Outcome Measures

a. Primary outcome measures

The primary outcome measure will be obtained in brain scans as the amount of radioligand binding quantified as distribution volume (V_T). Calculated from both brain and plasma data, V_T reflects the density of PDE4, corrected for any individual differences in metabolism of the radioligand or regional blood flow in brain.

b. Secondary outcome measures

The secondary outcome measure will be obtained in whole body scans as area under the curve (AUC) of radioactivity expressed as standard uptake value (SUV). SUVs are calculated by normalizing radioactivity in PET images to injection activity and body weight. Although AUC of SUV is not as fully quantitative as V_T , the AUC is widely used in clinical studies where arterial data are not obtained. If patients and healthy controls have markedly different clearance of $[^{11}C](R)$ -rolipram, group comparison using AUC of SUV may include errors. To correct group difference in clearance, in whole body imaging, venous concentrations of $[^{11}C](R)$ -rolipram will be measured at several time points. MRI measures of brain morphology including gray matter, white matter and CSF volume and folding will be estimated from the MRI images.

c. Tertiary outcome measure

The third outcome measure will be the difference in SUV between the baseline and the blocked whole-body scans. SUV is calculated as stated above.

10. Statistical Analysis

a. Analysis of data/ study outcomes

PET and MRI images will be co-registered for anatomic definition of brain regions. Brain and plasma data will be analyzed with compartmental and graphical modeling to calculate $V_{\rm T}$, which is proportional to the density of receptor or enzyme. $V_{\rm T}$ will be calculated both for regions of the brain and on a voxel basis. PET whole body images will be analyzed by drawing organs and by calculating AUC of SUV. For comparisons between subjects with MAS and healthy controls in brain and peripheral organs, an unpaired test, such as t- and Mann-Whitney tests will be used. In addition, in peripheral organs of MAS, for comparisons of PET data between affected and unaffected organs, a paired test will be applied if the contralateral side is unaffected. If contralateral side is also affected or not available, an unpaired test will be applied to compare the same tissue/organ between patients and healthy controls. For the statistical analyses, SPSS, PMOD, SPM, Freesurfer or equivalent programs will be used.

b. Power analysis

This is an exploratory study focusing on PET imaging. Clinical data obtained under 98-D-0145 may be used to interpret the relationship between PET findings and clinical manifestations of the disease. Although constitutive activation of $G_s\alpha$ is expected to increase cAMP signaling, which increases PDE4 levels, PDE4 levels in MAS are not known in postmortem tissue either in brain or in peripheral organs such as bone. Therefore, we cannot do a realistic power calculation.

To achieve the goals of this exploratory study, we request a total of 35 subjects: ~10 MAS subjects to undergo brain PET scan, ~10 MAS subjects to undergo whole body PET, and 15 healthy controls to undergo a brain scan and/or a whole body PET scan. By limiting subjects with MAS to those who have craniofacial fibrous dysplasia and neuropsychological symptoms, we expect to increase the likelihood of detecting changes in PET in this small sample size. To limit the number of study participants, all MAS and healthy subjects will be asked if they would be willing to have both brain and whole body PET scans. A smaller number of 15 healthy subjects are requested because healthy subjects are more likely to have both brain and whole body scans. Our previous study of [¹¹C](*R*)-rolipram brain scans in healthy subjects found that the coefficient of variation (SD/mean) of VT was 19%. Based on the activation of G_sa, we hypothesize that MAS patients will show increased rolipram binding for whichever one-sided test is appropriate. Assuming a 20% dropout from 10 subjects (thus, eight subjects per group) plus a 19% coefficient of variation (SD/mean) will provide a power of 0.80 to detect a 19% increase.

11. Human Subjects Protection

a. Subject selection

The study will be open to all racial and ethnic groups and will not target any particular group. Healthy volunteers will be recruited to match the patient group for age. Those who are HIV positive are excluded because the possible viral effects on the brain could interfere with interpretation of the outcome of the study.

b. Justification for exclusion of children

We will exclude children younger than 18 years of age to avoid radiation exposure to minors because the risks of radiation exposure outweighs the benefits.

c. Justification for inclusion of other vulnerable subjects

No population of vulnerable subjects will be included. Pregnant and breastfeeding females will be excluded because of greater risks of radiation to fetus and babies. Subjects without consent capacity will be excluded because this protocol has more than minimal risks and provides no direct benefits. Protections for NIH employees and staff participating in this study include 1) assuring that the participation or refusal to participate will have no effect, either beneficial or adverse, on the subject's employment or position at the NIH, 2) giving employees and staff who are interested in participating the "NIH Information Sheet on Employee Research Participation" prior to obtaining consent, and 3) assuring that there will be no direct solicitation of employees or staff.

d. Justification for sensitive procedures

This protocol does not include sensitive procedures such as use of placebo, medication withdrawal, provocative testing, or deception.

e. Safeguards for vulnerable populations and sensitive procedures

Pregnancy testing and interview will be performed for females with childbearing potential to prevent the enrollment of pregnant females. This protocol may enroll NIH employees. Protections for NIH employees and staff participating in this study include 1)

assuring that the participation or refusal to participate will have no effect, either beneficial or adverse, on the subject's employment or position at the NIH, 2) giving employees and staff who are interested in participating the "NIH Information Sheet on Employee Research Participation" prior to obtaining consent, and 3) assuring that there will be no direct solicitation of employees or staff.

When reviewing responses to the SCID, experienced clinical interviewers will supervise interviewers. Although rare, should the study staff identify symptoms of suicidality or suicidal ideations during the interview procedures, all necessary steps will be taken. The on-call clinician will be contacted to provide further evaluation, the subjects' own clinician may be notified after permission is granted by the subject. If not, other referral sources are provided and followed up, and necessary treatment steps (e.g., hospitalization, referral to a care provider, etc.) will be offered. However, NIH does not pay for outside hospitalization if that is required.

12. Anticipated Benefit

This study offers no direct benefit to individual subjects, but will lead to generalizable knowledge about MAS.

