Outcome measures: The primary outcome measure will be obtained in brain scans as the amount of radioligand binding quantified as distribution volume ($V_{\rm T}$). Calculated from both brain and plasma data, $V_{\rm T}$ reflects rolipram binding to PDE4, corrected for any individual differences in metabolism of the radioligand or regional blood flow in brain. The secondary outcome measure will be obtained in whole body scans as area under the curve (AUC) of radioactivity expressed as standard uptake value (SUV). SUV is calculated by normalizing radioactivity in PET images to injection activity and body weight. $V_{\rm T}$ in brain will be compared between subjects with MAS and healthy controls. AUC will be compared within-subjects with MAS between areas of craniofacial fibrous dysplasia and adjacent unaffected bone. AUC of whole body scans will also be compared between subjects with MAS and healthy controls. We hypothesize that subjects with MAS will show greater rolipram binding than healthy controls in brain regions, as well as greater rolipram uptake in bones affected by fibrous dysplasia than in unaffected bones. The third outcome measure will be the difference in SUV between the baseline whole body scan and the blocked (after roflumilast) whole body scan. This will help determine the amount of specific $[^{11}C](R)$ -rolipram binding in the periphery. We hypothesize that the $[^{11}C](R)$ -rolipram signal in the blocked scan will be greatly reduced, indicating that a majority of the signal in the baseline scan is specific

Table of Contents

1.	Introduction	6
2.	Study Objectives	10
3.	Subjects	11
4.	Study Design and Methods	12
5.	Management of Data and Samples	16
6.	Additional Considerations	17
7.	Risks and Discomforts	17
8.	Subject Safety Monitoring	19
9.	Outcome Measures	20
10.	Statistical Analysis	21
11.	Human Subjects Protection	21
12.	Anticipated Benefit	24
13.	Classification of Risk	24
14.	Consent Documents and Process	24
15.	Data and Safety Monitoring	25
16.	Quality Assurance	25
17.	Reporting of Unanticipated Problems, Adverse Events and Protocol Deviations	26
18.	Alternatives to Participation	26
19.	Privacy	26
20.	Confidentiality	26
21.	Conflict of Interest	27
22.	Technology Transfer	27
23.	Research and Travel Compensation	27
24.	References	29
25.	Attachments/ Appendices	31

List of Abbreviations

AUC	area under the curve
cAMP	3', 5'-cyclic adenosine monophosphate
MAS	McCune-Albright syndrome
MDD	major depressive disorder

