PET imaging of phosphodiesterase type 4 (PDE4) using $[^{11}C](R)$ -rolipram has been successfully used to study the in vivo activity of the cAMP cascade. PDEs hydrolyze the second messengers cAMP and cyclic guanosine monophosphate (cGMP) to terminate signal transduction. Eleven PDEs exist in the human body. PDE4 is selective to cAMP and is present in both brain and peripheral organs such as heart, lungs, kidney (5), immune cells (6), osteoclast (7), and osteoblast (8). Rolipram is a selective inhibitor of PDE4; PDE4 has four isozymes, and rolipram is not selective among these isozymes.

Our studies—described below—demonstrated that $[^{11}C](R)$ -rolipram PET is a valuable method of detecting cAMP cascade activity in living human and animal subjects. Because PDE4 is present in almost all brain regions and no regions without PDE4 are available to use as a reference to measure rolipram binding, we used $[^{11}C](R)$ -rolipram concentrations in arterial plasma (i.e., metabolite-corrected arterial input function) to measure rolipram binding in brain (9, 10). We also showed that rolipram binding can be accurately measured using only four arterial samples (9).

Broadly, the cAMP theory of depression posits that depression is caused by low cAMP signaling. The corresponding theory regarding the relevant mechanism of treatment is that chronic, but not acute, administration of antidepressants upregulates cAMP signaling. Although the cAMP theory of depression has limited supporting data, evidence for the mechanism of antidepressants has repeatedly been confirmed in animal studies. Chronic, but not acute, administration of all classes of antidepressants, as well as electroconvulsive therapy, upregulates several components of the cAMP pathway, including PDE4.

PDE4, an important component of the cAMP cascade, selectively metabolizes cAMP in the brain to the inactive monophosphate. Rolipram is a reversible inhibitor of PDE4, and binding of $[^{11}C](R)$ -rolipram provides a measure of the activity of this enzyme in brain. Due to a feedback mechanism, *in vivo* binding of $[^{11}C](R)$ -rolipram reflects the activity of the cAMP cascade; essentially, increased cAMP stimulates protein kinase A (PKA), which phosphorylates PDE4 that, in turn, increases rolipram binding.

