Taken together, these results elucidate two important and related points. First, the cAMP cascade, as indirectly measured with PDE4 binding, was downregulated in unmedicated patients with MDD. Second, antidepressant treatment normalized this $[^{11}C](R)$ -rolipram downregulation. These studies suggest that PDE4 inhibition, perhaps via subtype selective agents, might again be assessed for efficacy in MDD; the results also broadly support the cAMP theory of depression and of antidepressant action.

PDE4 inhibitor roflumilast

There are currently two FDA approved PDE4 inhibitors on the market: roflumilast (Daliresp) and apremilast (Otezla). Both are marketed as anti-inflammatory, but the former is indicated for chronic obstructive pulmonary disease, while the latter is used to treat psoriasis/ psoriatic arthritis. The side effect profiles for both drugs are similar in that the primary complaint is gastrointestinal (Table 1). While both drugs could be suitable for this study, roflumilast has been investigated more thoroughly in rodents and humans than apremilast. Therefore, we can better estimate an appropriate dose of roflumilast for this study based on previous experiments and clinical trials. A study conducted in non-human primates found that 200 μ g roflumilast resulted in a plasma concentration similar to peak concentration in humans (approximately 5 – 9 ng/ml) (14). This study hypothesized that a 500 μ g dose in humans would result in a PDE4 occupancy of 30-40%. The recommended dose of roflumilast is 500 μ g per day, with or without food. Maximum plasma concentrations occur approximately 1-2 hours after dosing depending on food consumption. The half-life of roflumilast and its primary metabolite, roflumilast N-oxide, are approximately 17 and 30 hours, respectively.

[figure not shown]
	Roflumilast		Apremilast	
	(500 mcg daily over 6 - 12)	Placebo	(30 mg BID over 1 -5 days in	Placebo
	months in N=4438)		N=497).	
Diarrhea	9.5%	2.7%	9.3%	1.2%
Weight decreased	7.5%	2.1%	NR	NR
Nausea	4.7%	1.4%	7.4%	1.4%
Headache	4.4%	2.1%	4.8%	1.8%
Back pain	3.2%	2.2%	NR	NR
Influenza	2.8%	2.7%	0.6%	0.6%
Dizziness	2.1%	1.1%	NR	NR
Decreased appetite	2.1%	0.4%	NR	NR
Vomiting	NR	NR	0.8%	0.4%

Table 1. Adverse reactions reported in $\geq 2\%$ of patients

BID, twice a day; NR, not reported

Table modified from (15) and (16)

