The purpose of this study is to assess whether uptake in dysplastic bone reflects parent radioligand binding to the enzyme or merely accumulation of radiometabolites, which are expected to have no affinity for the enzyme. For this purpose, we need not administer a receptor saturating dose of roflumilast, as the Lassen occupancy plot has great sensitivity to measure the percentage occupancy and then to extrapolate to 100% occupancy (Cunningham et al., *J. Cereb. Blood Flow & Metab.*, 30: 46-50, 2010). The sensitivity derives from the fact that it is a within subject comparison of multiple regions (in brain or periphery) at baseline and after blockade. We have used the Lassen plot numerous times, including to measure the occupancy of PDE4D subtype by the therapeutic candidate BPN14470. The figure below shows that that the occupancy (i.e., slope) is ~65% and the nondisplaceable uptake (V_{ND} or x-intercept) is ~4.9 mL \cdot cm⁻³.

2. Study Objectives

This study will investigate cAMP signaling in the brains of individuals with MAS using $[^{11}C](R)$ -rolipram PET imaging.

a. Primary objectives

We will study PDE4 levels in patients with MAS by comparing $[^{11}C](R)$ -rolipram binding in various brain regions between patients and age-matched healthy controls. In addition, in whole body imaging of patients with MAS, we will compare $[^{11}C](R)$ rolipram uptake between areas of fibrous dysplasia and adjacent unaffected bones. In whole body scans, we will also compare $[^{11}C](R)$ -rolipram uptake in peripheral organs between subjects with MAS and healthy controls. The reason for doing the latter comparison is that some tissues of MAS may contain the *GNAS* mutations even if there are no obvious structural changes.

b. Secondary objective

In order to quantify the amount of $[^{11}C](R)$ -rolipram binding in patient whole body scans, we will perform a blocking scan with 500 µg roflumilast, a FDA approved PDE4 inhibitor. Because of potential differences in metabolism of $[^{11}C](R)$ -rolipram in in the periphery of healthy controls and patients, it is difficult to interpret whether or not the $[^{11}C](R)$ -rolipram uptake is specific. By performing a blocking scan, we can quantify the amount of specific $[^{11}C](R)$ -rolipram binding to determine if there is a difference between healthy controls and patients.

3. Subjects

a. Description of study populations

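### The blocked-scan outcome is a raw SUV difference with no plasma or occupancy term and no lesion contrast, so it cannot show whether uptake in dysplastic bone is PDE4 binding

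*Combined protocol and SAP*

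**What the plan says.** Section 1 (PDE4 inhibitor roflumilast) gives the question: "The purpose of this study is to assess whether uptake in dysplastic bone reflects parent radioligand binding to the enzyme or merely accumulation of radiometabolites". It accepts a non-saturating dose because "the Lassen occupancy plot has great sensitivity to measure the percentage occupancy and then to extrapolate to 100% occupancy". The same section cites a primate study that hypothesised that the planned "dose in humans would result in a PDE4 occupancy of 30-40" percent.

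Section 2b gives the blocked scan a second use: to quantify specific peripheral binding and compare patients with controls.

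The outcome itself is in Section 9c: "The third outcome measure will be the difference in SUV between the baseline and the blocked whole-body scans". Section 9b defines the unit: "SUVs are calculated by normalizing radioactivity in PET images to injection activity and body weight". Section 9c names no region, plasma correction or occupancy analysis. The Précis predicts that the "signal in the blocked scan will be greatly reduced, indicating that a majority of the signal in the baseline scan is specific".

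Section 10a describes patient-control tests and affected-versus-unaffected tests, but nothing for baseline versus blocked. Section 4d.iii does provide a venous line to measure tracer at the blocked scan. Section 9b, however, assigns the venous data only to clearance differences between patients and controls.

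**The concern.** The question concerns the nature of the extra signal in a lesion. The outcome records only how far total signal moves. Three things are mixed in that movement: blockade of binding that ordinary bone also has, blockade of any binding peculiar to the lesion, and any change in tracer delivery between scans.

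Both kinds of error are possible. A fall could be credited to lesion PDE4 when only ordinary bone binding was blocked. A small fall, or a rise, could be read as non-specific uptake when binding is real. The baseline bone finding depends on this step for its interpretation, and participants accept a further radioligand injection and a drug dose to obtain it.

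**Working it through.** The plan states no sample size, effect or test for this outcome, so there is no figure to reproduce. The only input from the documents is occupancy, o = 0.30 to 0.40. The specific fraction of baseline signal (f), the relative change in plasma parent tracer (r) and the tissue values are assumptions.

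**1. No plasma change.** Blocked/baseline SUV = 1 − o·f.
- f = 1: a fall of 30% (o = 0.30) or 40% (o = 0.40), the largest possible.
- f = 0.50: a fall of 15% or 20%.
- Read in reverse, f = fall/o. A 15% fall means f = 0.15/0.30 = 0.50 or 0.15/0.40 = 0.375. Without an occupancy estimate, the difference cannot say whether most of the signal is specific.

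**2. Lesion excess, still no plasma change.** Assume unaffected bone has nondisplaceable signal 1.0 and specific signal 0.5 (total 1.5), and the lesion totals 2.5. The excess of 1.0 is either all specific (nondisplaceable 1.0, specific 1.5) or all radiometabolite (1.0 + 0.5 + 1.0). The baseline lesion:bone ratio is 2.5/1.5 = 1.667.

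| o | Excess | Lesion, blocked | Lesion change | Bone, blocked | Ratio, blocked | Ratio change |
|---|---|---|---|---|---|---|
| 0.30 | specific | 1 + 0.7×1.5 = 2.05 | −18% | 1.35 | 1.519 | −9% |
| 0.30 | radiometabolite | 1 + 0.7×0.5 + 1 = 2.35 | −6% | 1.35 | 1.741 | +4% |
| 0.40 | specific | 1 + 0.6×1.5 = 1.90 | −24% | 1.30 | 1.462 | −12% |
| 0.40 | radiometabolite | 1 + 0.6×0.5 + 1 = 2.30 | −8% | 1.30 | 1.769 | +6% |

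Lesion SUV falls under both hypotheses. The ratio moves in opposite directions.

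**3. With a plasma change.** If all signal scales with parent plasma, blocked/baseline SUV = (1 + r)(1 − o·f). The fall is cancelled at r* = o·f/(1 − o·f).

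| o | f = 0.25 | f = 0.50 | f = 0.75 | f = 1 |
|---|---|---|---|---|
| 0.30 | 8% | 18% | 29% | 43% |
| 0.40 | 11% | 25% | 43% | 67% |

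Example: o = 0.30 and f = 0.50 give −15.0% at r = 0, +2.0% at r = 0.2 and +10.5% at r = 0.3.

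**4. A Lassen plot on raw SUV.** Regress baseline minus blocked SUV on baseline SUV, with a common nondisplaceable value ND. The slope is o(1 + r) − r and the x-intercept is ND·o(1 + r)/slope. At o = 0.30 and r = 0.2, the slope is 0.36 − 0.20 = 0.16 instead of 0.30, and the intercept is 0.36/0.16 = 2.25 times ND. At r = 0.5 the slope is 0.45 − 0.50 = −0.05. The plot therefore needs plasma-normalised uptake.

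**5. Limits of the ratio.** Keep the values of step 2 with o = 0.30, and let the radiometabolite excess stay fixed while parent plasma rises. The ratio is 1 + 1/[1.35(1 + r)]. It drops below 1.667 once 1.35(1 + r) > 1.5, that is r > 11%. At r = 0.2, 0.3 and 0.4 it changes by −3.0%, −5.8% and −8.3%, which resembles binding. If lesion and bone share the same specific fraction, both shrink by the same factor and the ratio does not move, although binding is present.

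**The case against.** The strongest defence is that the protocol considered more than a subtraction. The Lassen plot is in the rationale, tracer is measured in venous blood at the blocked scan, and Section 9b recognises that clearance differences can distort SUV. The study also calls itself exploratory, and this is its third outcome. All of that stands, and a reader who inferred from Section 9c that nothing else was contemplated would be wrong. But the outcome and analysis sections make no use of the plot, and the stated use of venous data does not extend to baseline versus blocked.

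Three stronger readings are tempting and not supported:

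- **That roflumilast raises plasma tracer.** Section 1 says that PDE4 "is present in both brain and peripheral organs such as heart, lungs, kidney", so a change on systemic blockade is conceivable. The documents give neither its direction nor its size. Steps 3 and 4 are conditional on it; steps 1 and 2 are not.
- **That the scan serves only the lesion question.** Section 2b also needs it for the patient-control comparison. Controls have no lesion, so a lesion:bone ratio cannot be the main measure for that purpose.
- **That the ratio alone would settle the question.** Step 5 shows that it can fall without lesion-specific binding and stay flat when binding is present. Section 10a also foresees patients whose contralateral side is affected or unavailable. The blocked scan is optional with no planned number, so the power of any paired test is unknown.

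**Conclusion.** The concern holds as a mismatch between question and outcome. With no plasma change at all, the raw SUV difference neither isolates the lesion's excess (18% versus 6% falls at 30% occupancy on the assumed tissue values) nor shows directly that most of the signal is specific (a ceiling of 30-40%). A plasma rise of about 8% to 29% at 30% occupancy would cancel the fall for specific fractions of 0.25 to 0.75, if such a rise occurs.

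The result rests on the protocol's occupancy range, which is a hypothesis from a primate study whose title concerns brain, so peripheral occupancy may differ. The tissue values are illustrative. This should be corrected because the data needed are largely planned already. It does not affect the primary brain outcome.

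**What to change.** Amend Sections 9c and 10a as follows.

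1. Compare baseline and blocked scans on uptake AUC divided by that scan's venous parent-tracer AUC. Specify the Lassen analysis on this normalised uptake, and state its assumption of a common nondisplaceable value across regions. Use the normalised measure for the patient-control comparison in Section 2b.
2. Predefine the lesion and unaffected-bone regions. Report the paired change in log lesion:bone AUC ratio as lesion-specific supporting evidence, not as the sole decision rule. Read it with the plasma parent levels of both scans and, where measured, the radiometabolite levels.
3. Keep the raw SUV difference as descriptive.

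The cost is some extra analysis on scans and venous samples already planned, plus assay work if radiometabolites are quantified. Patients without usable unaffected bone will have no ratio. The limits in step 5 remain and should be stated in the plan. Normalising to parent plasma does not remove them: a radiometabolite signal that does not follow parent plasma is still distorted when divided by it.
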